4.9.5 Missing Data

Descriptive statistics will be run on missing data and checked for patterns. We anticipate few missing data issues other than possibly a few data points missing completely at random, as patients who enroll in the switching are choosing to receive their only course of MS treatment at no cost to them. Treatment is administered in clinic once every 24 weeks and is important to the patient, so patient compliance should not be much of an issue, unless they drop out of the study. Patients who miss a treatment will be followed up. Mixed models and GLMM (generalized linear mixed models) for longitudinal data can take into account missingness at random.

4.9.6 Determination of Sample Size

The sample size will be a convenience sample. It is anticipated a minimum of 100 patients will qualify for each cohort (200 total) resulting in studying 300 infusions with ocrelizumab and 200 infusions with rituximab. This is an observational study not designed to demonstrate superiority of ocrelizumab over rituximab in efficacy but instead indicate the magnitude of the relative tolerability and immunogenicity. The primary endpoint is the difference in the percentage of IRRs between the two study groups. In addition, both study groups will include treatment experienced patients on rituximab who have experienced a minimum of two infusions and either continue to stay on rituximab or switch to ocrelizumab.

To estimate study power with the proposed sample size of 100 infusions in each group, we conducted a chart review of 50 patients at the Rocky Mountain MS Center who are currently taking rituximab and examined their IRRs using the proposed IRR grading scale (see section 3.3.1) from Grade 0-5. The number and severity of IRRs were captured following their third rituximab infusion. The highest grade of an IRR that occurred during the infusion was recorded. Our pilot data revealed that following the third rituximab infusion, 14.3% of patients had an IRR of which 85.71% were Grade 0, 12.24% were grade 2 and 2.05% were Grade 3. Hauser et al., found that following the second infusion of rituximab in patients, the majority of whom (60%) were not taking a DMT for 6 months prior to initiating rituximab only 20.3% experienced in an IRR.³

Using IRR estimates from our pilot data and establishing a clinically meaningful difference of 20% increase in IRRs, we conducted the following power analysis for a sample of 95 patients (assuming a 5% attrition rate after recruiting 100 patients in each study group). An IRR proportion for ocrelizumab users at 34.3% compared with 14.3% for rituximab (obtained from our pilot data) for a two sided (alpha = 0.05) two sample proportion test for the null hypothesis of no difference between rituximab and ocrelizumab in proportion of IRRs would result in 90% power for 95 patients per group.

In response to the FDA IND letter, “the power analysis in Section 4.9.6 of the protocol appears to compare the infusion-related reaction (IRR) rate at the third rituximab infusion (14.3%) to that of the first infusion of OCR (34.3%). Because

the incidence of an IRR for most monoclonal antibodies is highest with the first infusion and declines with subsequent infusions, we recommend that you revise your sample size and power calculations using the IRR incidence for a comparable number of infusions; for example, the first, second, or third infusion”:

Our response is that neither the switching and comparison groups are receiving their very first infusion of any anti-CD 20 monoclonal antibody (rituximab or ocrelizumab) following enrollment in the study. Both study groups have received a minimum of at least two infusions of rituximab prior to enrollment in the study. The first study related infusion for ocrelizumab in the switching group represents (at minimum) their third infusion for an anti-CD monoclonal antibody which will be compared to their third standard of care infusion for rituximab (at minimum) following study enrollment. As a result, we believe both groups represent those patients who have experienced at least three infusions of an anti-CD monoclonal antibody agent. Thereby our power calculations were based on the IRRs observed following the third infusion of rituximab in our pilot sample (at 14.3%) and using a clinically meaningful difference of 20% increase in IRRs for the ocrelizumab group (34.3%) to provide 90% power for 95 patients per study group (assuming a 5% attrition rate after recruiting 100 patients in each study group).

As there is only one primary outcome to power the study on, there is no need to reduce the alpha level of the univariate test as part of multiple testing adjustment. Adjustment for interim analysis is not an issue as there are no early stopping rules.

4.10 Data Quality Assurance

Accurate, consistent, and reliable data will be ensured through the use of standard practices and procedures.

5. REPORTING OF ADVERSE EVENTS

5.1 Assessment of Safety

Safety Review

All AEs and SAEs will be reviewed by the project Steering Committee at their monthly project management meetings. This Committee will be composed of Drs. [name], [name] and [name] supported by [name] PhD and the lead study coordinator, [name]. We will also establish an external DSMB as required by UCD that will meet at baseline, then every 6 months and at the time of any SAE. This committee will consist of two neurologists and [name] PhD biostatistics.

Adverse Events

An AE is any unfavorable and unintended sign, symptom, or disease temporally associated with the use of an investigational medicinal product (IMP) or other

protocol-imposed intervention, regardless of attribution. For the patients on Ocrelizumab, all AEs occurring between the time of consent and the study termination visit will be recorded.

For the comparator group, IRRs are the only AEs that will be collected. In addition, clinical relapses documented during the clinical process will also be collected.

Serious Adverse Events

An AE should be classified as an SAE if the following criteria are met:

- It results in death (i.e., the AE actually causes or leads to death).
- It is life threatening (i.e., the AE, in the view of the investigator, places the subject at immediate risk of death. It does not include an AE that, had it occurred in a more severe form, might have caused death.).
- It requires or prolongs inpatient hospitalization.
- It results in persistent or significant disability/incapacity (i.e., the AE results in substantial disruption of the subject's ability to conduct normal life functions).
- It results in a congenital anomaly/birth defect in a neonate/infant born to a mother exposed to the IMP.
- It is considered a significant medical event by the investigator based on medical judgment (e.g., may jeopardize the subject or may require medical/surgical intervention to prevent one of the outcomes listed above).

All SAEs reported or observed in either group will be recorded and reported as necessary.

5.2 Methods and Timing for Assessing and Recording Safety Variables

The investigator is responsible for ensuring that all AEs and SAEs that are observed or reported during the study, are collected and reported to the FDA, appropriate IRB(s), and Genentech, Inc. in accordance with CFR 312.32 (IND Safety Reports).

Adverse Event Reporting Period

The study period during which all AEs and SAEs must be reported begins after informed consent is obtained and initiation of study treatment or "initiation of any study procedures" and ends at T₃ which is 6 months after last dose of study medication. After this period, investigators should only report SAEs that are attributed to prior study treatment.

Assessment of Adverse Events

AEs and SAEs may be collected from medical record review, or elicited by asking non-directive questions at each study visit both before and after the infusion. Infusion-related AEs will be captured by the infusion nurses as well as self-reported by the patient as described in Outcome Measures. Patients will also be reminded to alert the study team about any concerning health issues between study visits. Each recorded AE or SAE will be described by its duration (i.e., start and end dates) and will include, and actions taken.

For all recorded AEs, a study investigator will make an assessment of seriousness, and causality. To ensure consistency of AE and SAE causality assessments, investigators should apply the following general guideline:

Yes

There is a plausible temporal relationship between the onset of the AE and administration of the ocrelizumab, and the AE cannot be readily explained by the subject's clinical state, intercurrent illness, or concomitant therapies; and/or the AE follows a known pattern of response to the ocrelizumab; and/or the AE abates or resolves upon discontinuation of the ocrelizumab or dose reduction and, if applicable, reappears upon re-challenge.

No

Evidence exists that the AE has an etiology other than the ocrelizumab (e.g., preexisting medical condition, underlying disease, intercurrent illness, or concomitant medication); and/or the AE has no plausible temporal relationship to ocrelizumab administration (e.g., event diagnosed 2 days after first dose of ocrelizumab).

Expected adverse events are those adverse events that are listed or characterized in the Package Insert or current Investigator Brochure.

Unexpected adverse events are those not listed in the Package Insert (P.I.) or current Investigator Brochure (I.B.) or not identified. This includes adverse events for which the specificity or severity is not consistent with the description in the P.I. or I.B. For example, under this definition, hepatic necrosis would be unexpected if the P.I. or I.B. only referred to elevated hepatic enzymes or hepatitis.

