Earlier concepts of MS disease pathology have suggested that pathogenic T cells are sufficient for the full expression of MS. However, it is now evident that full autoimmune B cells and humoral immune mechanisms also play key roles.⁵ Ocrelizumab is a humanized monoclonal antibody that targets CD20 and selectively depleted CD-20 expressing B cells. CD20 is a B cell surface molecule that is expressed on pre B cells and mature B cells, but not expressed earlier in the development of B cells or on mature plasma cells. In all three ocrelizumab studies (with relapsing and progressive populations), treatment with 600 mg of ocrelizumab led to rapid and complete depletion of circulating CD19⁺ B cells within 14 days post treatment.⁴ B cell depletion was sustained throughout treatment period. The median time to repletion of B cells was 72 weeks (range 27-175 weeks). We hypothesize that in switching rituximab treated patients to ocrelizumab, the proportion of patients with B cell depletion (CD19⁺ and CD20⁺ ≤ 1%) 6 months after the first and third infusion of ocrelizumab will be the same as the baseline assessment which will be 6 months after the last dose of rituximab and similar to findings in OPERA I and II.

Immunogenicity results from the OPERA I and II trials examined the number of patients who had treatment induced anti-drug antibodies (ADA) to ocrelizumab.⁴ Of the 807 patients who received ocrelizumab and had an ADA assay from a post baseline sample during the controlled treatment period, 3 patients (0.4%) showed treatment induced ADA to ocrelizumab. Of these, 1 patient tested positive for neutralizing antibodies (NAB) to ocrelizumab. During the open label extension phase, the prevalence of ADA continued to remain low with post baseline incidence of 1.9% (2/103 with treatment induced ADA). Currently there is little evidence examining the prevalence of treatment induced ADAs to both rituximab and ocrelizumab in patients that switch from the former to the latter in comparison to continuing rituximab patients. Therefore, we will perform assays to detect ADAs to both rituximab and ocrelizumab in all patients switching from rituximab to ocrelizumab at Day 1, 6 months and between 12 and 18 months on ocrelizumab.

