4.5.1 Assessments during Treatment

The following evaluations will be conducted during and post treatment:

Study Visits and Procedures Summary:

Study visits for the switching group include a) screening visit, b) first infusion of 300 mg of ocrelizumab (day 1 or T₀), c) 300 mg of ocrelizumab infusion on day 15 (T₁), d) 600 mg of ocrelizumab at 6 months (+/- 2 weeks) after day 1 (T₂) and, e) a research termination visit between month 12 and 18 - (+/- 2 weeks)(T₃). In some cases, screening procedures may be performed on the first infusion day rather than as a separate visit. The patient may continue on 600 mg of ocrelizumab or (if the patient prefers) 500mg rituximab at T₃, or 12 to 18 months after Day 1 (T₀). A month is defined as 28 days. Study visits for the comparator group include only standard of care infusion of rituximab, up to two infusions per patient, approximately 6 months apart. Research data on IRRs for the comparator group will be collected from the medical records.

A summary of all procedures for switching group is outlined under “Schedule of Events” in **Table 1** below. During the screening visit, patients will be consented for the study and receive both a medical and full neurological exam. Verification of their hepatitis B and C status including testing will be conducted if a patient has not been tested in the last two years. MS disease history and demographic information will also be collected. Patients will also receive an EDSS exam and take an online version of the PDDS (done as standard of care- on an iPad).

The Expanded Disability Status Scale (EDSS) is a commonly used assessment that allows clinicians to objectively measure changes in the disability status of MS patients using unbiased clinical raters.⁷ The **EDSS** provides a total score on a scale that ranges from 0 to 10. The first levels 1.0 to 4.5 refer to people with a high degree of ambulatory ability and the subsequent levels 5.0 to 9.5 refer to the loss of ambulatory ability. The range of main categories include (0) = *normal neurologic exam*; to (5) = *ambulatory without aid or rest for 200 meters; disability severe enough to impair full daily activities*; to (10) = *death due to MS*. In addition, it also provides seven subscale measurements called Functional System (FS) scores.

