(generalized linear mixed models) methods to incorporate correlation on repeated infusions on a patient. The same method will apply to other longitudinal binary outcomes. Poisson or negative binomial models with exposure terms could calculate rates of IRR per infusion per patient as a counting process. Similar methods will be used to compare IRR rates between the switching group and OPERA I and II phase 3 clinical trials. The total number of IRRs experienced in each patient, will be analyzed with Poisson or negative binomial models. Paired T tests will be used to assess differences in specific cytokine markers between pre and post infusion at each infusion cycle. Patient reported outcomes will also be reported descriptively. Frequencies and proportions will be reported for adverse and serious events and loss to follow up

As contingency methodology, exact tests and confidence intervals for measures of association between categorical variables can be utilized when necessary, if the sample sizes for some of the cells are small. Transforms or rank based methods, such as Wilcoxon sign rank, can be used in place of the T-test if deviation for normality is severe. Otherwise the T-test is a robust test of mean differences for medium to large sample sizes. If matching leads to good balance between the treatment groups on the demographic and disease variables, including age, MS disease duration, and baseline PDDS score, then confounding will not be an issue and the proposed unadjusted tests should be adequate. Alternatively, if the demographic and disease variables are not balanced, then regression or propensity score methods will be used to adjust for potential confounding. Sensitivity analysis comparing unadjusted and adjusted results will be used to determine the extent of the confounding effect. Adjustment for covariates can sometimes improve the precision of the estimated treatment difference by reducing random noise in the outcome.

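### Section 5.2 equates T3 with 6 months after the last dose when it falls 6 to 12 months after, and Section 4.9.4 plans only crude AE proportions over unequal follow-up

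*Combined protocol and SAP*

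**What the plan says.** **End of the reporting period.** Section 5.2 closes AE and SAE reporting at T3, "which is 6 months after last dose of study medication. After this period, investigators should only report SAEs" put down to earlier study treatment. Section 5.1 sets the window for ocrelizumab patients without a month count: "all AEs occurring between the time of consent and the study termination visit will be recorded".

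**Timing of the visits.** Section 4.5.1 lists T2 as "600 mg of ocrelizumab at 6 months (+/- 2 weeks) after day 1" and T3 as "a research termination visit between month 12 and 18", also with a two-week window. It adds: "A month is defined as 28 days". Table 1 shows ocrelizumab at T0, T1 and T2 and none at T3, so T2 is the last study dose. Section 3.1 explains the T3 range by delays in third-party payor approval of the 12-month dose. Sections 2.2 (antibodies) and 3.3.2 (B cells) put the final assessment six to twelve months after the last infusion.

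**Early stoppers.** Section 4.7 asks patients who discontinue ocrelizumab to stay in the study assessments to the end, for safety.

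**Analysis.** Section 4.9.4 says: "Frequencies and proportions will be reported for adverse and serious events". It mentions exposure terms only for IRR rates.

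**The concern.** Section 5.2 is the rule that staff follow when deciding whether an event must be reported, and it identifies the closing date in two ways that agree only when T3 falls at month 12. Under a literal 6-month reading, a non-serious AE, or an SAE not attributed to treatment, could fall outside the reporting period although it occurred before T3. Deaths regardless of attribution are tied to the same reporting period (Section 5.3 b). The mismatch is widest for the patients whom Section 4.7 deliberately keeps under observation.

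The analysis raises a second issue, which remains even if T3 is taken as the end point. A crude proportion of patients with an AE rises with time observed, and observation time here depends partly on payor approval. AEs other than IRRs, with infections as the named example, are a stated secondary objective in the switching group (Section 2.2 c). The reported percentages would refer to no single length of follow-up.

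**Working it through.** **Inputs.** Month = 28 days; T2 = month 6 ± 14 days; T3 = months 12 to 18 ± 14 days (all Section 4.5.1). Dates are counted from Day 1.

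- T2 = 6 × 28 = day 168 (window 154 to 182).
- T3 = 12 × 28 to 18 × 28 = day 336 to 504 (window 322 to 518).

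**1. The plan's own figure.** With T3 at month 12, 336 − 168 = 168 days = 6.0 months. The statement in Section 5.2 is reproduced only at the early end of the T3 range.

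**2. The full range.**

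| Case | T3 − T2 (days) | Weeks | Months |
|---|---|---|---|
| T3 at month 12 | 336 − 168 = 168 | 24 | 6.0 |
| T3 at month 18 | 504 − 168 = 336 | 48 | 12.0 |
| Shortest with windows | 322 − 182 = 140 | 20 | 5.0 |
| Longest with windows | 518 − 154 = 364 | 52 | 13.0 |

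The nominal rows match the six to twelve months in Sections 2.2 and 3.3.2.

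**3. Distance between the two end points.** For a month-18 T3, six months after the last dose is day 168 + 168 = 336, against T3 at day 504. The difference is 168 days, or 24 weeks.

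**4. Early stopper.** If the Day 15 infusion (14 days after Day 1) is the last one, T3 comes 336 − 14 = 322 to 504 − 14 = 490 days later (11.5 to 17.5 months). Beyond the 168-day clause this leaves 322 − 168 = 154 to 490 − 168 = 322 days, that is 22 to 46 weeks. At any given T3 the gap is 22 weeks longer than for a patient treated at T2.

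**5. Unequal follow-up.** Day 1 to T3 is 336/7 = 48 to 504/7 = 72 weeks, a ratio of 1.5. With windows it is 322/7 = 46 to 518/7 = 74 weeks, a ratio of 1.6.

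**6. Possible effect on a crude proportion.** The documents give neither AE risks nor the share of late visits, so this is an illustration. Assume a constant rate and risk p by week 48. The risk by week 72 is 1 − (1 − p)^1.5. For p = 0.20 this is 1 − 0.80^1.5 = 0.284. If a share s of patients has T3 at month 18 and the rest at month 12, the pooled proportion is (1 − s) × 0.200 + s × 0.284:

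- s = 0: 20.0%
- s = 0.2: 21.7%
- s = 0.5: 24.2%
- s = 1: 28.4%

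**The case against.** The strongest reply is that T3 is the end point throughout. Section 5.2 says the period ends at T3, and the 6-month clause merely describes that visit. Section 5.1 ends AE recording at the termination visit, and Table 1 schedules AE recording there. Section 5.2 also opens by requiring all AEs and SAEs seen during the study to be collected and reported, and Section 5.3 i sends SAEs to the manufacturer whether related or not. This stands, and it shows how the conflict should be settled. It does not make the clause correct, and the clause sits in the reporting rule itself.

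A reader might infer that events will be lost. The documents do not show this: it would follow only if the 6-month clause were taken to override the other text. Nor do they suggest variation between sites, since all patients are treated at one centre.

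On the analysis, it is fair to say that the aim is descriptive. For the comparator group, Section 5.1 collects only IRRs, documented relapses and SAEs. Unequal follow-up for non-serious AEs other than IRRs therefore lies within the switching group and biases no between-group comparison of those events. Event start and end dates are recorded (Section 5.2), so rates could be computed later. That makes the addition cheap, but the plan still does not provide for it.

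Two further inferences are tempting. One is that 24 weeks is too short because the Introduction cites B-cell repletion from 27 weeks (median 72). Nothing in the documents ties AE collection to repletion, and even a nominal month-18 T3, 48 weeks after T2, comes before that median. The other is that a table cut at 24 weeks after T2 would equalise follow-up. It would not, because the windows allow T3 as early as 20 weeks after T2.

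**Conclusion.** The point holds on two counts. First, the interval in Section 5.2 is wrong for any patient whose T3 falls later than month 12. It conflicts with Sections 2.2, 3.3.2 and 4.5.1, and the two end points differ by up to 24 weeks nominally, or 46 weeks for a patient who stops after Day 15. Second, crude AE and SAE proportions pool patients whose follow-up differs about 1.5-fold.

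The effect is confined to the descriptive safety summary, mainly in the switching group. The primary endpoint is counted per infusion and is unaffected. So is the power: 95 per group with 14.3% against 34.3% gives 0.901, which agrees with the stated 90%.

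The size of the distortion is unknown. A reader might take a move from 20% to 28% as the expected error, but 28% would arise only if every patient had T3 at month 18. The 20% base risk and the constant rate are assumptions. The change is worth making because it is cheap and concerns a reporting rule and a stated objective; the primary conclusion is not in danger.

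**What to change.** In Section 5.2, delete the 6-month clause, or reconcile it so that the section matches 5.1: all AEs and SAEs in ocrelizumab patients, whatever their attribution, up to each patient's actual termination visit. State that this also covers patients who stop ocrelizumab but remain in follow-up under Section 4.7.

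In Section 4.9.4, keep the crude proportions and add one of the following for AEs other than IRRs, SAEs and infections:

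- events per 100 patient-years, with person-time running to T3 or withdrawal; or
- cumulative incidence of the first event at a common time from Day 1, censoring patients whose T3 comes earlier.

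The second option assumes that the timing of T3 is unrelated to AE risk. Payor delay, the reason given in Section 3.1, makes that plausible, but the reasons for late visits should be tabulated. Report the distribution of follow-up time in either case. IRRs stay in their per-infusion analysis.

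The cost is a wording change and one extra analysis. It needs no new visits, because event dates are already recorded.

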Safety data from the Investigators Brochure on the OPERA I and II phase 3 trials comparing ocrelizumab to interferon β -1a on relapsing MS patients showed that IRRs were the most common adverse events experienced by patients treated with 600 mg of ocrelizumab.⁴ The percentage of patients experiencing IRRs was higher in the ocrelizumab group (relapsing forms of MS: 34.3%; primary progressive forms of MS 39.9%) compared with the interferon β -1a (active control) group who received placebo infusions (relapsing forms of MS: 9.7%; primary progressive forms of MS: 25.5%). The rate of IRRs was highest during the first infusion or Dose 1 (27.5% on Day 1; 4.71% on Day 15 of Dose 1) and decreased over time (13.7%; 9.6% and 7.8% following Dose 2, 3, and 4 respectively) for the ocrelizumab treated group. Comparatively, interferon β -1a users experienced 6.5% of IRRs on Day 1, 2.58% on Day 15, \leq 2.00% after doses 2, 3 and 4 respectively. The reported IRRs were primarily mild-to-moderate in severity (Grades 1 and 2). Serious IRRs occurred in 0.1% and 1.0% respectively of relapsing and progressive patients and treated with ocrelizumab.

Clinical data describing the efficacy and tolerability profile of rituximab and ocrelizumab has utilized populations with different prior treatment characteristics. In the phase 2 HERMES trials, a majority (78.5%) of rituximab patients had been **previously been treated** with a disease modifying therapy in the last 2 years.³ In contrast, the OPERA I and II phase 3 clinical trials, a majority of ocrelizumab

patients (72.9% in OPERA I and 73.8% in OPERA II) represented a **treatment naïve population**.⁴ Examining IRRs in patients who have switched from rituximab to ocrelizumab versus those continuing on rituximab will evaluate the magnitude of the IRRs and subsequent tolerability of ocrelizumab in a real world population of MS patients previously been exposed to rituximab.

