After completion of the infusion, the IV cannula should remain in situ for at least 1 hour to allow for administration of drugs intravenously, if necessary, in the event of a delayed reaction. If no adverse events occur during this period of time, the IV cannula may be removed and the patient may be discharged. See the Ocrelizumab Investigator's Brochure for detailed instructions on drug preparation, storage, and administration.

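### Section 5.2's only example of implausible timing is an unnamed event diagnosed 2 days after the first ocrelizumab dose, which permits coding an early reaction as unrelated

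*Combined protocol and SAP*

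**What the plan says.** Section 5.2 has a study investigator judge seriousness and causality for every recorded adverse event. It offers a general guideline, meant to keep those causality judgements consistent, with two answers.

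- **'Yes'** opens with timing: "There is a plausible temporal relationship between the onset of the AE and administration of the ocrelizumab", provided nothing else readily explains the event. Another route to 'Yes' is that "the AE follows a known pattern of response to the ocrelizumab". A third rests on improvement after the drug is stopped or reduced.
- **'No'** has two grounds. The first is that "Evidence exists that the AE has an etiology other than the ocrelizumab", illustrated by a list of other kinds of cause. The second is that "the AE has no plausible temporal relationship to ocrelizumab administration (e.g., event diagnosed 2 days after first dose of ocrelizumab".

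No other section gives a time window or a second example of implausible timing. Section 5.2 also states: "Each recorded AE or SAE will be described by its duration (i.e., start and end dates".

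On when reactions occur, the Introduction says: "The rate of IRRs was highest during the first infusion or Dose 1 (27.5% on Day 1; 4.71% on Day 15 of Dose 1". Section 4.3.1 keeps the cannula in place for at least an hour after the infusion "to allow for administration of drugs intravenously, if necessary, in the event of a delayed reaction".

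**The concern.** The one timing example in a guideline written for consistency will influence how it is applied. This example makes a 2-day interval after the first dose look implausible in itself, because it does not say what sort of event is meant. It also changes the reference date, from onset under 'Yes' to diagnosis under 'No'.

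The period just after the first ocrelizumab dose is central to a study of whether patients switched from rituximab have unexpected infusion reactions. If a serious and unexpected event in that period were coded as unrelated, a report that depends on relatedness could be misclassified or delayed. Infusion reactions are not excluded merely because they are listed in the brochure: section 5.2 counts as unexpected also "adverse events for which the specificity or severity is not consistent with the description in the P.I. or I.B".

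**Working it through.** The documents state no figure to reproduce, so the check is of the text, with a little arithmetic for scale.

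1. **Reference date.** Take an event with onset on Day 1, during or soon after the first infusion, and diagnosis on Day 3 (Day 1 + 2 days). Judged on onset, the interval from dosing is 0 days and the timing ground for 'Yes' can apply. Judged on diagnosis, the interval is 2 days, which matches the 'No' example exactly. The same event can be pointed either way. The gap between the two dates is realistic: section 5.3 asks for a diagnosis in place of symptoms where one is known, and for a diagnosis made later to be sent as follow-up.

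2. **Type of event.** The example may have been meant for a condition that could not have developed in 2 days. It may equally be read as covering any event. The text does not choose between these readings.

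3. **Fit with the protocol's own account.** The Introduction gives ocrelizumab reaction rates of 27.5% on Day 1, 4.71% on Day 15, and 13.7%, 9.6% and 7.8% after Doses 2, 3 and 4. Day 1 is therefore 27.5 / 4.71 = 5.8 times the Day 15 rate and 27.5 / 13.7 = 2.0 times the Dose 2 rate. The Introduction also describes rapid B-cell depletion, complete within 14 days of treatment. The severity scale in section 3.3.1 places prolonged reactions, recurrence after improvement, and renal or pulmonary sequelae in Grade 3, and these can plausibly be diagnosed after the infusion day.

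4. **Where relatedness decides, and where it does not.**

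| Turns on relatedness | Does not turn on relatedness |
|---|---|
| FDA 7-day report (5.5) | Recording of all adverse events in ocrelizumab patients (5.1) |
| FDA 15-day report (5.5) | SAEs and events of special interest sent to the manufacturer within one business day (5.3, item i) |
| Prompt IRB notice of serious, unexpected drug reactions (6.4) | Deaths in the reporting period (5.3, item b) |
| Post-study SAE reports (5.2; 5.3, item f) | Steering Committee and DSMB review (5.1) |
| | General reporting duty (5.2) and keeping the IRB informed of significant events (6.4) |
| | Nurse-graded reaction endpoint (3.3.1) and planned analyses (4.9) |

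   The post-study route is the most remote. An event 2 days after the first dose falls inside the study period unless the patient has left the study almost at once.

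5. **Scale.** The plan is for 100 switching patients, each with one first dose, so the example applies literally on about 100 occasions, plus any replacements. The Introduction puts serious infusion reactions at 0.1% of relapsing patients treated with ocrelizumab: 100 × 0.001 = 0.1 expected. That figure comes from a largely treatment-naive population and excludes serious events that are not infusion reactions, so it only indicates that few cases would be in play.

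**The case against.** The strongest reply is that the operative test is plausibility, which is sound, and that the example only illustrates it. An investigator who sees symptoms begin during the infusion has the onset wording under 'Yes', and often the known-pattern ground too, and would probably code the event as related. This largely stands, and it is why the wording permits miscoding rather than compelling it. It is also fair that the rates by infusion and the one-hour cannula rule do not describe reactions on day 2. They show that the first infusion is when reactions are most expected, and no more.

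Three stronger readings are tempting and are not supported.

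- A reader might infer that the protocol sets a 2-day cutoff, or that all early post-infusion events are to be coded unrelated. It gives one illustrative time point and no cutoff.
- A reader might infer that a 'No' switches off the FDA reports. Section 5.5 states its own criteria and does not refer to the section 5.2 code, so an effect on those reports is possible but inferred.
- A reader might infer that the whole scheme fails because one event can meet grounds on both sides, or because Yes/No is not matched to the wording of the reporting rules. Those are details that investigators would settle by judgement, and the point here does not rest on them.

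What does not stand is the suggestion that the rest of section 5.2 cures the example. No passage corrects it. The known-pattern ground gives less cover for unexpected events, which are the ones subject to expedited FDA reports. The third 'Yes' ground relies on stopping the drug or reducing the dose, and section 4.3.2 does not permit dose modification. The committees review events, but nothing says that they re-judge causality codes.

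**Conclusion.** The example is wrong as written. It conflicts with the onset basis of the 'Yes' ground and fits poorly with the protocol's own account of first-infusion reactions. Confidence is high on the wording defect and lower on its consequences, which depend on an investigator taking the example literally and carrying that judgement into a report that turns on relatedness.

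The size is qualitative. The documents give no basis for a miscoding rate, few events are likely to be affected, and the number of planned analyses affected is zero. It is a minor point, worth making because the correction is simple and improves safety classification.

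**What to change.** Make two wording changes in section 5.2. Delete the parenthetical example, and refer the timing ground for 'No' to the onset of the event, as the timing ground for 'Yes' already does. The start date that section 5.2 requires for each event supplies the information, so no new data are needed. The causality judgement stays with the investigator.

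The cost is a short amendment and a note to investigators. The downside is that some events may move from unrelated to related, which could add to expedited reporting; the documents do not allow the number to be estimated.
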